## Non-interventional Study Protocol

Document Number:	c14514897-01
BI Study Number:	0205-0536
BI Investigational Product(s):	Tiotropium inhalation solution – Respimat Inhaler (Ba 679 BR Respimat)
Title:	Specific Use-Result Surveillance of Spiriva Respimat in asthmatics (patients with mild to moderate persistent asthma)
Brief lay title	Specific Use-result Surveillance of Spiriva Respimat® in mild to moderate persistent asthmatic patients
Protocol version identifier:	1.0
Date of last version of protocol:	Not applicable
PASS:	Yes
EU PAS register number:	To be registered
Active substance:	R03BB04 : Tiotropium
Medicinal product:	Spiriva® 1.25 µg Respimat® 60 puffs Spiriva® 2.5 µg Respimat® 60 puffs
Product reference:	Not applicable
Procedure number:	Not applicable
Marketing authorisation holder(s):	
Joint PASS:	No
Research question and objectives:	This PMS is designed: To investigate the safety and effectiveness of Spiriva Respimat in patients with mild to moderate persistent asthma under real-world use.
Country(-ies) of study:	Japan
Author:	

Marketing authorisation holder(s):	
MAH contact person:	
EU-QPPV:	
Signature of EU-QPPV:	The signature of the EU-QPPV is provided electronically
Date:	16 January 2017
Page 1 of 33	
Proprietary confidential information	
© 2019 Boehringer Ingelheim International GmbH or one or more of its affiliated companies. All rights reserved. This document may not - in full or in part - be passed on, reproduced, published or otherwise used without prior written permission	

## **2. LIST OF ABBREVIATIONS**

ADR	Adverse Drug Reaction
AE	Adverse Event
AESI	Adverse Event of Special interest
CA	Competent Authority
CCDS	Company Core Data Sheet
CI	Confidence Interval
CML	Local Clinical Monitor
CRA	Clinical Research Associate
CRF	Case Report Form
CTCAE	Common Terminology Criteria for Adverse Events
CTP	Clinical Trial Protocol
eCRF	Electronic Case Report Form
ENCePP	European Network of Centres for Pharmacoepidemiology and Pharmacovigilance
EU-QPPV	European Union – Qualified Person for Pharmacovigilance
FDA	Food and Drug Administration
FVC	Forced Vital Capacity
GCP	Good Clinical Practice
GEP	Good Epidemiological Practice
GPP	Good Pharmacoepidemiology Practice
GPSP	Good Post- marketing Study Practice
GVP	Good Pharmacovigilance Practices
IB	Investigator’s Brochure
IEC	Independent Ethics Committee
IRB	Institutional Review Board
J-PAL	Japanese Pharmaceutical Affairs Law
J-RMP	Japan Risk Management Plan
J-PSR	Japanese Periodic Safety Report
MedDRA	Medical Dictionary for Regulatory Activities
MAH	Marketing Authorisation Holder
NIS	Non-Interventional Study
PASS	Post-Authorization Safety Study
PMDA	Pharmaceuticals and Medical Devices Agency
PMS	Post Marketing Surveillance
SAE	Serious Adverse Event
TSAP	Trial Statistical Analysis Plan

### **3. RESPONSIBLE PARTIES**

#### Sponsor

#### 4. ABSTRACT

Name of company: Boehringer Ingelheim			
Name of finished medicinal product: Spiriva Respimat			
Name of active ingredient: Tiotropium bromide			
Protocol date: 16 January 2017	Study number: 0205-0536	Version/Revision: 1.0	Version/Revision date: NA
Title of study:	Specific Use-Result Surveillance of Spiriva Respimat in asthmatics (patients with mild to moderate persistent asthma)		
Rationale and background:	The safety of Spiriva® 1.25 µg Respimat® 60 puffs and Spiriva® 2.5 µg Respimat® 60 puffs (hereinafter referred to as Spiriva Respimat) in patients with mild to moderate persistent asthma under the real-world use was not confirmed in clinical trials.		
Research question and objectives:	This PMS is designed; To investigate the safety and effectiveness of Spiriva Respimat in patients with mild to moderate persistent asthma under real-world use.		
Study design:	Non-interventional, observational study based on new data collection		
Population:	Inclusion criteria: 
 
• Patients diagnosed with mild to moderate persistent bronchial asthma
 
• Patient aged ≥ 15 years old
 
• Patients who are naive to Spiriva Respimat and receive Spiriva Respimat for the first time for the treatment of bronchial asthma on top of at least ICS treatment.
 
		
Variables:	Demographics Medical history/baseline conditions Previous/concomitant therapies Pulmonary function test (peak expiratory flow rate, forced expiratory volume in 1 second, forced vital capacity), if available Asthma severity and asthma control status, if available ACQ 6 score, if available Spiriva Respimat administration Adverse event Safety laboratory test (if corresponding AEs are reported)		
Data sources:	Patients data will be gathered by electronic Case Report Form on EDC		
Study size:	150 (safety set)		
Data analysis:	Descriptive		
Milestones:	Final report will be prepared by 31 July 2019		

## **5. AMENDMENTS AND UPDATES**

None

Number	Date	Section of study protocol	Amendment or update	Reason
-	-	-	-	-

## 6. MILESTONES

Milestone	Planned Date
Start of data collection	01 July 2017
End of data collection	31 December 2018
Study progress report	None
Study interim report 1	08 January 2018 (J-PSR)
Study interim report 2	08 January 2019 (J-PSR)
Study interim report 3	17 February 2019 (re-examination report for Spiriva Respimat in asthmatics)
Registration in the EU PAS register	To be registered
Final report of study results:	31 July 2019

## **7. RATIONALE AND BACKGROUND**

Tiotropium is one of the most widely used long-acting bronchodilators worldwide for the treatment of COPD (including chronic bronchitis and emphysema), and now, after systematic clinical investigation, it is proposed to be designated for relief of various symptoms associated with the obstructive impairment of airways due to bronchial asthma.

Tiotropium delivered via the Respimat® inhaler once daily demonstrated consistent and significant improvement in lung function parameters in the Phase III trials despite the fact that the requirement for stable asthma maintenance therapy at baseline and throughout the treatment period might impose limitations on the effect size that can be achieved with an additional treatment. In addition to the improvements in lung function, patients who remained symptomatic despite treatment with high-dose ICS+LABA or medium-dose ICS were shown to have a symptomatic benefit from taking tiotropium.

Tiotropium delivered via the Respimat® inhaler once daily also demonstrated long-term safety and tolerability compared with that of placebo when administered at a daily dose of 2.5 and 5 µg to adult patients with asthma. Exposure to tiotropium in the clinical program covered more than 1000 patient-years in more than 2200 patients. The overall frequencies of AEs, drug-related AEs, and SAEs were similar across all treatment dose groups in trials with the same duration and patient population. In general, no specific concerns with regard to abnormal vital signs were raised for patients who took tiotropium. There were no patterns of increased particular AEs for the tiotropium treatment groups compared with that of placebo in any subgroup analysis. No deaths were reported during the entire clinical program. According to the current guidelines for the treatment of asthma, although various treatment options are available for long-term asthma management including ICS as the first-line therapy and other additional therapies depending on asthma severity (e.g., LABA, leukotriene receptor antagonist, theophyllines, antihistamines, oral steroids, anti-IgE), improvement of symptoms is insufficient in many patients (i.e., uncontrolled and/or at potential risk of asthma exacerbation), and there is a growing medical need for additional therapeutic options for the treatment of asthma. Responding to the medical needs, inhaled administration of anticholinergic bronchodilator tiotropium is a new additional maintenance therapy in patients with asthma who remain symptomatic despite treatment with at least ICS. Treatment with tiotropium improves lung function and symptoms of asthma patients more appropriately and may be an important paradigm shift in the treatment of asthma patients.

### **Japanese regulation related to Post Marketing Surveillance (PMS)**

This PMS is planned according to the Japanese Law for Ensuring the Quality, Efficacy, and Safety of Drugs and Medical. The law requires in principle that data on the safety and effectiveness of all launched products to be accumulated under real-world clinical practice. The data collected in the PMS are required to be submitted to the Pharmaceuticals and Medical Devices Agency (PMDA), the local regulatory agency in Japan, according to the process of re-examination which will take place 10 years after approval of registration. The PMS is a part of the local Risk Management Plan in Japan (J-RMP) to be submitted to PMDA at New Drug Application.

## **8. RESEARCH QUESTION AND OBJECTIVES**

The objective of this PMS is to investigate the safety and effectiveness of Spiriva Respimat in patients with mild to moderate persistent asthma under real-world use.

## **9. RESEARCH METHODS**

### **9.1 STUDY DESIGN**

Non-interventional observational study based on newly collected data under real-world use.

### **9.2 SETTING**

#### **9.2.1 Study sites**

will nominate the candidate sites which satisfied the following criteria and ask the nominated sites to participate in the study.

- Spiriva Respimat has been delivered to the site.
- The observation of peak expiratory flow meter is done as part of the usual medical practice.

Planned number of sites: Approximately 25 Sites

A medical representative will explain the objectives, subjects and methods of the surveillance to the investigator at the site and exchange a written contract with the head of the site (e.g., hospital director).

#### **9.2.2 Study population**

##### **9.2.2.1 Inclusion/Exclusion criteria**

###### Inclusion criteria:

- Patients diagnosed with mild to moderate persistent bronchial asthma
- Patient aged  $\geq 15$  years
- Patients who are naive to Spiriva Respimat and receive Spiriva Respimat for the first time for treatment of bronchial asthma on top of at least ICS treatment.

\*:Asthma severity is defined by “Table 6 Classification of asthma severity based on the present treatment (adult)” of “Japanese Guideline for Adult Asthma 2014”[[P14-15105](#)].

###### Exclusion criteria:

- Patients who have a contraindication to Spiriva Respimat defined in the package insert for Spiriva Respimat
- Patients who have been enrolled in this study before.

##### **9.2.2.2 Patient registration method**

The registration method will be a continuous investigation system. Patients who begin treatment with Spiriva Respimat after the conclusion of the contract will be registered by

entering necessary information in the EDC within 14 days whenever possible from the day of treatment initiation (inclusive).

The necessary variables for registration are gender, date of birth, start date of administration and the reason for use. And ICS treatment as of inclusion criteria will be checked in the EDC system.

Patient registration will be stopped when the target number of the study is reached. After the end of the registration period, investigators use a signed form to confirm that patients have been registered continuously at the site. A log of all patients included into the study will be maintained at the site.

#### 9.2.2.3 Registration period

From July 2017 to June 2018

### 9.2.3 Study visits

After start of the treatment with Spiriva Respimat, each patient will be observed for 12 weeks or at premature discontinuation from the PMS. Observations are made at the following time points: before first administration of Spiriva Respimat (this visit is defined as baseline), 4 weeks and 12 weeks after the start of treatment, or at discontinuation.

### 9.2.4 Study discontinuation

reserves the right to discontinue the PMS overall or at a particular study site at any time for the following reasons:

1. Failure to meet expected enrolment goals overall or at a particular study site
2. Emergence of any efficacy/safety information that could significantly affect continuation of the PMS.
3. Violation of Good Post-marketing Study Practice (GPSP) or the contract of a study site or investigator, thereby disturbing the appropriate conduct of the PMS.

The investigator / the study site will be reimbursed for reasonable expenses incurred in case of PMS termination (except in case of the third reason).

## 9.3 VARIABLES

### 9.3.1 Exposures

This PMS is conducted under real-world use of Spiriva® 1.25 µg Respimat® 60 puffs and Spiriva® 2.5 µg Respimat® 60 puffs following the labeling (Japanese package insert).

### 9.3.2 Outcomes

#### 9.3.2.1 Primary outcome

The primary Outcome is the absolute and relative (%) frequency of patients with suspected adverse drug reactions (ADRs).

Safety will be assessed by use of the following other parameters of interest:

- Adverse events irrespective of seriousness
- Laboratory tests (if corresponding AEs are reported)

There is no primary outcome for effectiveness as the primary objective of a PMS is evaluating safety.

#### 9.3.2.2 Secondary outcome

- Change from baseline in asthma control status at Week 12

##### Asthma control status:

Asthma control status will be assessed based on the “Asthma prevention and management guideline” [ [P14-15105](#)]

#### 9.3.2.2: 1 Asthma control status Table

Patients control status	Well-controlled	Insufficiently-controlled	Poorly-controlled
	Meet all the criteria	Meet 1 or 2 criteria	Meet all of 3 Criteria
Asthma symptoms (in the daytime or at night)	None	Once or more a week	Once or more a week
Use of reliever	None	Once or more a week	Once or more a week
Limitation of activities, including exercise	None	Restricted	Restricted

### **9.3.3 Covariates**

The investigator will enter the following patient data into the eCRF for registration.

- Patient's ID, gender, date of birth, start date of administration, indication, asthma severity

#### **Demographics**

##### At baseline:

Patient background including weight, height and smoking history

Medical history/baseline conditions

(Ischaemic heart disease, Cardiac failure, Myocardial infarction, Angina pectoris, Cardiac arrhythmia, Renal failure)

Previous /concomitant therapies

Pulmonary function test (PEFR (peak expiratory flow rate), FEV1 (forced expiratory volume in 1 second), FVC (forced vital capacity), if available

Asthma severity and asthma control status, if available [ [P14-15105](#)]

ACQ 6 score, if available

Spiriva Respimat® administration, dose

##### At week4:

Concomitant therapies

Pulmonary function test (PEFR, FEV1, FVC), if available

Asthma severity and asthma control status, if available [ [P14-15105](#)]

ACQ 6 score, if available

Spiriva Respimat® administration, dose, particularly any changed in dose with details provided

##### At week12:

Concomitant therapies

Pulmonary function test (PEFR, FEV1, FVC), if available

Asthma severity and asthma control status, if available [ [P14-15105](#)]

ACQ 6 score, if available

Spiriva Respimat® administration, dose, particularly any changed in dose with details provided

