#### **9.5 STUDY SIZE**

It is planned to enroll 180 patients with mild to moderate persistent asthma to ensure the number of 150 patients as safety analysis set at least.

150 (safety set)

150 patients will be set as a safety analysis set. The main ADR (about 2.0%) in clinical trials were asthma (1.8%), dysphonia (1.8%) and dry mouth (1.8%). With 150 patients, the incidence of the main adverse events would be evaluated.

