### ANNEX 3. FLOW CHART OF VARIABLES

#### 1. Observation period

Item \ Time	Observation period 		
	Before first administration of Spiriva Respimat	4W	12W (or at discontinuation)
Patient registration	X 		
Patient demographics	X		
Administration of Spiriva Respimat	X (to be recorded throughout the observation period)		
Medical history/baseline conditions	X		
Previous/concomitant therapies	X (to be recorded throughout the observation period)		
Pulmonary function test			
FEV 1	(X)	(X)	(X)
FVC	(X)	(X)	(X)
PEFR 	(X)	(X)	(X)
Asthma severity	X		
Asthma Control Status	(X)	(X)	(X)
QOL (ACQ 6 score)	(X)	(X)	(X)
Adverse events	X (to be recorded throughout the observation period)		
Laboratory tests  associated with AE		(X)	
EDC transmitted time 		X	

(X): If applicable

- 1: Time points during the observation period are approximate. Collected data should be reported as of the closest available visit.
- 2: Patients administered Spiriva Respimat will be registered within 14 days from whenever the day of first administration is possible.
- 3: PEFR is defined as the mean of the PEFR values of the 7 days before each visit.
- 4: When laboratory related AE is reported, Laboratory tests associated with AE are reported.
- 5: eCRF (electronic case report form): Data are to be transmitted immediately after being entered into the eCRF at 12 weeks after the start of treatment or at discontinuation. In case of occurrence of any adverse events, the data should be immediately entered into the eCRF and transmitted.

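### The only visible secondary outcome, change in asthma control status at Week 12, depends on two entries that the protocol makes optional although they need no test

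*Protocol*

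**What the plan says.** Protocol Section 8 states the objective as "to investigate the safety and effectiveness of Spiriva Respimat in patients with mild to moderate persistent asthma under real-world use". Section 9.3.2.1 ranks the two parts: "There is no primary outcome for effectiveness as the primary objective of a PMS is evaluating safety". Section 9.3.2.2 then names one secondary outcome, "Change from baseline in asthma control status at Week 12".

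Section 9.3.3 lists the item with the same condition at baseline, Week 4 and Week 12: "Asthma severity and asthma control status, if available". The abstract carries the same condition. Annex 3 gives asthma control status a bracketed mark at all three times, explained in the legend as "X): If applicable". Asthma severity, also a clinical classification, has a plain X at baseline there.

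The control status table in Section 9.3.2.2 uses three items: symptoms, reliever use and limitation of activities. It contains no lung-function item.

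On the analysis side:
- SAP 6.6 leaves missing effectiveness data unimputed.
- SAP 6.3 admits a patient to the effectiveness set with a baseline and at least one on-treatment value of control status, PEFR, FEV1, FVC or ACQ 6.
- SAP Table 7.5.2: 1 assigns Unknown when either control status is missing.
- SAP 7 by default computes percentages over all patients in the set, with or without a value.

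**The concern.** A change from baseline exists only for patients with a status at both visits, and the protocol requires neither. It treats the item like spirometry, where recording only what is available makes sense because a device and a procedure are needed. Control status needs only three questions, and Annex 3 shows that the protocol can require a clinical classification when it chooses to.

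What is at stake is how the secondary result can be read. Neither document gives an expected or minimum number of patients with paired status, and the limitations in Protocol 9.9 do not mention missing effectiveness data. If recording depends on how the patient is doing, the observed change describes a selected subset. The collected data could not show by how much it differs from the whole.

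**Working it through.** **Inputs from the documents.** Protocol 9.5: "It is planned to enroll 180 patients with mild to moderate persistent asthma to ensure the number of 150 patients" in the safety set, and a main ADR rate of about 2.0% (1.8% for each named reaction). No availability figure for control status is given.

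**Assumptions.** A share f of 150 patients has status at both baseline and Week 12, and 50% of those are improved. Both are illustrative.

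**Step 1: what the 150 stands for.** The protocol states no criterion. Assume a 95% chance of seeing at least one event.
- At 2.0%: n = ln(0.05)/ln(1 - 0.02) = 148.3, so 149. With 150 patients the chance is 1 - 0.98^150 = 0.952.
- At 1.8%: n = ln(0.05)/ln(1 - 0.018) = 164.9, so 165. With 150 patients the chance is 0.934.

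The 150 is therefore a safety figure and is not disputed here. Going from 180 to 150 allows for 30/180 = 16.7% loss. No corresponding figure exists for the secondary outcome.

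**Step 2: how a patient is counted without the outcome.** Take a patient with PEFR at baseline and Week 12 but no control status. SAP 6.3 places this patient in the effectiveness set, SAP 6.6 imputes nothing, and Table 7.5.2: 1 returns Unknown. This is a realistic route, because Protocol 9.2.1 selects sites where "The observation of peak expiratory flow meter is done as part of the usual medical practice".

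**Step 3: what missing pairs do to the result.** The lower bound counts every missing patient as not improved: 0.5f. The upper bound counts every one as improved: 0.5f + (1 - f). The sampling half-width is 1.96 × sqrt(0.25/n).

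| f (assumed) | paired n of 150 | 95% half-width among observed | bounds for all 150 |
|---|---|---|---|
| 100% | 150 | ±8.0 points | 50% |
| 90% | 135 | ±8.4 points | 45-55% |
| 70% | 105 | ±9.6 points | 35-65% |
| 50% | 75 | ±11.3 points | 25-75% |

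From f = 90% to f = 50% the half-width grows by about 3 points, while the bounds widen from 10 to 50 points. The main loss is in what can be said about the unrecorded patients, not in sampling precision.

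**Step 4: both visits are needed.** If status is available in 70% at each visit, independently, 0.70 × 0.70 = 49% are paired, about 74 of 150. Without independence the paired share lies between 0.70 + 0.70 - 1 = 40% and 70%. At 95% per visit, independently, it is 0.95 × 0.95 = 90%, about 135 of 150.

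**The case against.** The study records usual care, and collecting an item only where it exists is a coherent choice for such a study. Safety is primary, the study size rests on ADRs, and the analysis is descriptive. The SAP does not hide the gap: patients in the effectiveness set without a pair appear as Unknown and stay in the denominator. All of that stands. It limits the weight of the point but does not put a value where none was recorded.

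A reader might infer more than the documents support:
- *That the recorded patients are self-selected.* Nothing says why status would be absent. It may simply follow site habit. Selection is a risk, not a documented fact.
- *That required fields would secure status for nearly all patients.* No completeness figure is given, patients may discontinue, and visit times are approximate. The table also runs from none to at least weekly, so symptoms or reliever use less often than weekly have no place in it. Three answers will not always give a category.
- *That the effectiveness part of the objective rests on this item alone.* PEFR, FEV1, FVC and ACQ 6 are collected too, also optionally.
- *That selecting sites on peak flow secures the wrong variable.* SAP Table 6.3: 1 refers to further endpoints, and sections that may define them are not visible. PEFR may be one of them.
- *That no later analysis can help.* Bounds and a comparison of patients with and without pairs are later analyses, and useful ones. They describe the uncertainty but do not remove it.

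Two practical objections also have force. Protocol 9.10.2.1 requires eCRF data to come from source documents, so a required field means asking and charting as well as entry. And on the planned dates, registration ended in June 2018, so 12-week observation would end around September, before the revised SAP of 19 October 2018. If collection is already complete, only the reporting part of the fix can still be applied.

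**Conclusion.** The point holds as a cheap improvement to a secondary outcome. The only visible secondary outcome depends on two optional entries, although its components need no test. The SAP displays the resulting gap without filling it. The documents do not allow the gap to be sized. At assumed paired availability of 90%, 70% and 50%, with 50% improved among those observed, the bounds for all 150 patients are 10, 30 and 50 points wide. The primary safety outcome is unaffected. The conclusion rests on the collection rules as written and on these illustrative values. It does not rest on any claim that recording will in fact be selective.

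**What to change.** 1. **Annex 3:** change Asthma Control Status from (X) to X at baseline and at 12W/discontinuation. Week 4 may stay optional.
2. **Protocol 9.3.3 and abstract:** remove the availability condition for asthma control status at those two times. It shares a line with asthma severity, so the line should be split.
3. **eCRF:** make the three components required fields at both times, with not assessed plus a reason as the only alternative. Leave spirometry, PEFR and ACQ 6 optional.
4. **SAP 7.5.2 and report:** give the number with paired status, compare patients with and without it on baseline characteristics, and show best- and worst-case bounds beside the observed change.

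The cost is protocol, eCRF and SAP wording, plus a small charting and entry burden at two visits. No test or procedure is added, and the study stays observational. Completeness should improve but is not guaranteed, since not assessed remains a permitted answer.
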